Official title: Clinical Evaluation of Bulk-fill Restorative Materials

NCT number and document date: NCT06109987 and 18/04/2024

This study was conducted at the Restorative Dentistry Department of the University from December 2021 to July 2023 after the Ethics Committee of Recep Tayyip Erdogan University (2021/201) approved the study protocol. The clinical study has also been registered at ClinicalTrials.gov with the identifying number NCT06109987.

Participant selection

The study recruited participants who received routine dental treatment at the university's dental clinic. In order to be eligible for the clinical trial, individuals were required to meet the following criteria: being in a state of good general health, being over the age of 18, having a minimum of 20 teeth that are correctly positioned, and having at least one primary carious lesion (class I, II, or V) that requires restorative treatment. The study excluded patients with removable prostheses, inadequate oral hygiene leading to multiple caries, periodontal and gingival disease, uncontrolled parafunctional behaviours, severe bruxism, and dentin hypersensitivity. Furthermore, those who were taking medication, undergoing orthodontic treatment, pregnant, or feeling spontaneous pain were not included in the study.

One dental expert evaluated 160 individuals to determine their eligibility. The clinical assessments were conducted by a mouth mirror, a periodontal probe, and an explorer while the area was well-lit. A total of 14 patients were excluded from the study: 10 due to failure to satisfy all the inclusion criteria and four due to their refusal to participate. A total of 146 patients were determined to be eligible. Patients who agreed to participate in the study were apprised in detail about its goals and potential problems. The participation of patients was entirely voluntary, and all participants gave their written informed consent forms.

Cavity preparation and restorative procedures

Characteristics of the teeth were examined and recorded before the restorative procedure. Periapical radiographs were used to determine the status and extent of the carious and any potential periodontal or periapical pathology that may require endodontic treatment. The teeth that received treatment were vital, symptom-free, and in occlusal contact. All participants received their teeth cleaned using a rubber-cup with a pumice slurry, then washed to remove all remnants of debris or plaque. After that, a shade guide was employed to determine the color of the restorative materials. Local anaesthetic (Ultraver D-S Forte, Beykoz, Istanbul) was applied to prevent sensitivity or pain during operations.

To prepare the cavities, diamond fissure or spherical burs (Wilofa Diamant, Willi Lohmann, Germany) were used in a high-speed handpiece (Kavo, Biberach, Germany) with copious water cooling. Soft dentin tissues were removed by a tungsten-carbide round bur (Ela, Engelskirchen, Germany) at a low-speed until hard dentin was detected using an excavator. Cavity preparation is limited only to removing tooth tissues affected by caries. Extra retention or bevels were not prepared on the cavity walls to prevent unnecessary loss of tooth structures. The bevels were created only when class V cavities were to be restored with the composite material (SonicFill 2) up to 1 mm at the enamel margins. Cavity preparation did not include cusps; the cavity depths ranged from 2 to 5 mm. After finishing the cavity preparation, the cavity was washed with an air-water spray and dried by the cotton pellet. The matrix system (Dispodent Sectional Matrix, Istanbul, Turkey) and appropriate wedges were placed in class II cavities.

A universal adhesive (Ambar Universal Bond, FGM, Brazil) was applied to cavities in the self-etch technique consistent with the manufacturer directives (Table 1) prior to the placement of a bulk-fill composite material (SonicFill 2; SF2; Kerr, Orange, USA). The first layer of the adhesive was applied vigorously by scrubbing for 10 s, followed by a second layer for 10 s. It was then lightly air-dried for 10 s to allow the solvent to evaporate. Next, the

adhesive agent was light-cured for 10 s by an LED unit (VALO, Ultradent, Utah, USA) with a 1000 mW/cm² power output. Regardless of the type of cavity, the prepared cavities were filled with a single composite piece up to 5 mm, which was then polymerized twice for 20 s. Occlusion control was performed using articulation paper (Alfred Becht, Carl-Zeiss, Offenburg, Germany), followed by corrections using fine and ultra-fine diamond burs (Wilofa Diamant, Willi Lohmann, Germany). Finishing and polishing procedures were completed with polishing rubbers (Dien Fong Silicon Rubber Polisher, Shenzhen, China) at low speed under water cooling.

Before placing Equia Forte HT (EFHT; GC, Tokyo, Japan), 20% polyacrylic acid conditioner (Cavity Conditioner, GC, Tokyo, Japan) was applied for 10 s, followed by removal with a wet-cotton pellet. Then, the cavity was gently dried with cotton. EFHT and ChemFill Rock (CR; Dentsply Sirona, USA) capsules were placed in the automatic mixer by pressing with a finger, mixed for 10 s and 15 s, respectively, and injected into the cavity with a special capsule holder. The materials were condensed by a ball burnisher and waited to harden. Occlusion was checked with articulating paper. The corrections were performed with ultra-fine diamond finishing burs and then polished by polishing discs (OptiDisc, Kerr, Switzerland). With a micro brush, Equia Forte Coat (GC, Tokyo, Japan) was applied to EFHT restoration surfaces and then polymerized for 20 s. Surface coating was not used for ChemFill Rock restorations. The application methods and compositions of the materials are given in Table 1. All restorations were made by the same experienced operator.

Clinical Evaluation

The participants were called back after one week (T1), 6 (T2), and 18 (T3) months. Restorations were assessed in terms of retention and fracture, color or translucency match, marginal and surface staining, marginal adaptation, anatomic form, postoperative sensitivity, and secondary caries by modifying the World Dental Federation (FDI) criteria.²⁷ The estimated findings

received the following scores: clinically excellent (1), clinically very good (2), clinically good (3), clinically sufficient or satisfactory (4), clinically unsatisfactory (4), and clinically poor (5).

One qualified clinician assessed the restorations using a mirror and probe under a reflector light. He examined ten photos representing possible scores for each criterion before clinical evaluation. The postoperative sensitivity of the participants was evaluated by asking whether they had any pain throughout this period. Bite-wing and periapical radiographs were taken at 6- and 18-month evaluation periods. Periapical lesions, secondary caries, and compatibility with adjacent teeth were checked.

Statistical Analysis

Chi-square and Fisher Exact tests were performed to assess differences between restorative materials. Friedman and Wilcoxon Signed rank tests were performed to assess the effect of time on the restorations. Kaplan-Meier and Long-rank tests were also performed to determine the overall survival rates of the restorations. Survival rates were estimated by time to failure (4 or 5 scores) during clinical evaluation, regardless of color match and translucency criteria. The significance level was set at 0.05. The data was analyzed using statistical software (IBM SPSS 27.0; Chicago, IL, USA).

Results

A clinical flow diagram presenting the recruitment of participants is presented in Figure 1. Fourteen patients out of 160 did not meet the inclusion criteria and were excluded. One hundred forty-six patients (62 males and 84 females) were chosen, with a mean age of 28 (18-62). Initially, all patients participated (100%), but the participation rate fell to 89% in the 6-month evaluation. The participation rate further decreased to 79.4% in the 18-month evaluation. Finally, the last participation involved 116 patients, with 267 restorations being evaluated.

Table 2 displays the distribution of restorations based on jaws. Of the restorations, 59.9% (160) were placed in molars, and 40.1% (107) were placed in premolars. In terms of location, 48.3% (129) of the restorations were in the maxilla, and 51.6% (138) were in the mandible.

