3.1 Fracture and Retention

No loss of retention or fracture was observed in any restoration at baseline and 6-month follow-up. After the 18-month follow-up, 4 of the EFHT restorations (1 in class I or V and 2 in class II) were lost, and 1 (class II) was fractured (Table 3). Only one of the CR restorations (class II) was lost (Table 4). No loss of retention or fracture was observed in the SF2 restorations (Table 5). The type of cavity did not affect the performance of the restorative materials used ($p > 0.05$). EFHT (94.2%) showed significantly lower retention than SF2 (100%) after 18 months ($p = 0.019$), regardless of cavity type (Table 6). More restoration failures (de-bonding and fracture) were observed in class II cavities (4.4%) regardless of restorative material (Table 6), with no significant differences ($p = 0.26$). The Kaplan-Meier test presented significant differences among the survival rates of restorative materials over 18 months (Figure 2). The overall survival rates were 94.2% for EFHT, 98.8% for CR, and 100% for SF2 after 18 months.

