3.4 Color match and translucency

The color match between teeth and the materials differed significantly for restorative materials ($p < 0.001$, Tables 3-5). The color and translucency of EFHT restorations matched the teeth better compared to CR restorations ($p < 0.001$) but were worse than SF2 restorations ($p < 0.001$, Table 6, and Figure 3).

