3.7 Anatomic form

There were no significant differences in anatomical form between the materials at baseline and during all evaluations ($p > 0.05$), regardless of cavity type. Furthermore, no significant difference was found between the initial measurements and later recalls for any of the materials ($p > 0.05$) (Tables 3-5). After 18 months, achieving proper anatomical form was significantly more difficult in class I and II cavities compared to class V (Table 6 and Figure 3) ($p = 0.002$), regardless of restorative material type.

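### Does a single 0.05 level with no stated multiplicity rule undermine the claim that Equia Forte HT has lower retention than SonicFill 2?

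*Protocol*

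**What the plan says.** Under Clinical Evaluation the protocol lists the outcomes: "Restorations were assessed in terms of retention and fracture, color or translucency match, marginal and surface staining, marginal adaptation, anatomic form, postoperative sensitivity". The list ends with a further item, secondary caries, which makes seven criteria. Three materials are compared: Equia Forte HT (EFHT), ChemFill Rock (CR) and SonicFill 2 (SF2).

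The Statistical Analysis section states that "Chi-square and Fisher Exact tests were performed to assess differences between restorative materials", adds Kaplan-Meier and log-rank methods for survival, and closes with "The significance level was set at 0.05". It names no main criterion, no order of testing and no adjustment.

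The Results then report:

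- Section 3.1: EFHT "showed significantly lower retention than SF2 (100%) after 18 months ($p = 0.019".
- Section 3.1, after that: "The Kaplan-Meier test presented significant differences among the survival rates of restorative materials over 18 months", with no p-value.
- Section 3.4: "The color match between teeth and the materials differed significantly for restorative materials" (p < 0.001), followed by two pairwise results, each also p < 0.001.
- Section 3.7: no difference between materials in anatomic form, but "achieving proper anatomical form was significantly more difficult in class I and II cavities compared to class V" (p = 0.002).

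**The concern.** Three materials give three pairs, and seven criteria give 21 pairwise material comparisons before visits and cavity classes are counted. If 21 independent tests were each run at 0.05, the chance of at least one false positive would be 1 − 0.95^21 = 66%; for three tests it would be 1 − 0.95^3 = 14%.

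The retention result is the one that could be affected. The p of 0.019 lies below 0.05 but above 0.05/3 = 0.0167, the first Holm threshold for three pairs. A reader who expects Holm or Bonferroni would call it non-significant, and one who expects a global test first would call it significant. If the protocol leaves the rule open, the statement that one material retains worse than another seems to depend on a choice that nobody recorded.

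**Working it through.** **Inputs.** Section 3.1 gives 5 EFHT failures (4 lost, 1 fractured), 1 for CR and 0 for SF2, with survival of 94.2%, 98.8% and 100%. The opening of the Results gives 267 restorations in 116 patients at 18 months. Arm sizes are not in the text at hand, so they are inferred.

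**Arm sizes (assumption: conventional rounding).** 1 − 5/n = 94.2% holds only for n = 86. 1 − 1/n = 98.8% holds for n = 80 to 86. SF2 is then 267 − 86 − CR = 95 to 101.

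**Reproducing p = 0.019.** The two-sided Fisher test for 5/86 against 0/101 gives 0.0193, which prints as 0.019. The other splits give 0.0198 to 0.0227. The printed value is therefore consistent with a raw pairwise Fisher p at 86/80/101.

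**Retention under different rules**

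| Rule | Calculation | Result |
|---|---|---|
| Holm, Fisher | 3 × 0.0193 (other pairs 0.212 and 0.442) | 0.058, not significant |
| Holm, uncorrected chi-square | 3 × 0.0140 at 86/80/101 | 0.042, significant |
| Same, CR 81 to 86 | 3 × 0.0145 to 3 × 0.0172 | 0.0435 to 0.0515; above 0.05 only at CR = 86 |
| Global test, then pairs at 0.05 | global chi-square 0.0217, Freeman-Halton 0.0196, then pair 0.0193 | significant |

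Across all seven splits the global p is 0.0217 to 0.0221 (chi-square) and 0.0157 to 0.0213 (Freeman-Halton). Section 3.1 reports no failures at 6 months, so all fall at the 18-month visit and the log-rank p is about 0.022. Every version of the global test is below 0.05.

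**Why global-then-pairs is valid here.** With three materials, any two pairwise null hypotheses together imply that all three materials are equal. The closed test of a pair therefore needs only the global test and that pair, each at 0.05.

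**Actual inflation within retention.** Fisher tests on rare events are conservative. Enumerating all outcomes at 86/80/101 under a common failure rate, the chance that at least one of three ungated pairs reaches 0.05 is 4.2% at 6/267 = 2.2%, 8.0% at a 5% rate and 9.3% at a 10% rate.

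**Across criteria.** Colour (p < 0.001) survives even a factor of 21 (below 0.021). After colour, Holm on seven global tests leaves a limit of 0.05/6 = 0.0083, which retention misses. But at 18 months the document reports one marginal staining, one adaptation defect, no sensitivity and no secondary caries. With one event in 267, the smallest possible global p is 80/267 = 0.30, so these four cannot reject. Holm over the remaining three (retention, colour, anatomic form) leaves 0.05/2 = 0.025, which the global retention p of about 0.02 meets. The cavity-class result on anatomic form stays at 3 × 0.002 = 0.006 even if tripled.

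**Effect size.** 5/86 − 0/101 = 5.8 points; Newcombe 95% interval 0.9 to 12.9, and at the Bonferroni level of 98.3% it is −0.7 to 15.0.

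**The case for a change.** The strongest case for acting is that this document carries results. It does not merely leave a rule to another document; it sets a level, runs a pairwise contrast and publishes a verdict. Two respectable procedures disagree on that verdict. The overall survival difference comes after the pairwise claim, has no p-value and is not said to gate anything. The result is also thin: one SF2 failure would move the raw p to 0.096, and one fewer EFHT failure would give 0.043 for the pair and 0.055 for the global Freeman-Halton test.

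Much of this is true. The p-value is not labelled as raw or adjusted, and Holm on the Fisher values does give 0.058. Expected failures per arm are only about 2 (for example 6 × 86/267 = 1.9), so Fisher is a better choice than the chi-square that passes Holm.

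Three things limit it. First, disagreement between a valid procedure and a more conservative one is not an error, and the reported pattern (a global difference and pairs, for both retention and colour) fits the valid one. Second, fragility to one event is a matter of sample size and would remain under any multiplicity rule. Third, the raw-Fisher reading rests on rounding that the document does not always follow: 138/267 = 51.69% is printed as 51.6%. If the survival rates were truncated, EFHT would be 87 and CR 84 to 90. Fisher for the pair is then 0.023 to 0.027, and an uncorrected chi-square at 87/87/93 gives 0.0190. Tripled, either test then exceeds 0.05, but the global chi-square stays at about 0.024 and the closed test still rejects.

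**Conclusion.** No change is called for. The missing rule is detail that a statistical analysis plan commonly holds, and the choice between Holm and global-then-pairs is a fair trade-off. Under the second, the retention claim stands with a global p of about 0.02 on every arm split considered. Under Holm on Fisher values it would be 0.058. The familywise error of three ungated Fisher pairs is 4.2% at the observed pooled rate, so the inflation that the concern fears is largely absent for this criterion. The colour result holds under every rule.

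Little would be gained by adding a procedure now. The protocol says "This study was conducted at the Restorative Dentistry Department of the University from December 2021 to July 2023" and is dated April 2024, so any rule or main criterion named at this stage would be chosen after the data, and one of the two natural choices alters no conclusion. Saying whether 0.019 is unadjusted, and giving the global p and an interval for the 5.8-point difference, would be a courtesy to the reader of the report.

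This rests on inferred arm sizes, on Tables 3 to 6 not being in the text at hand (a note to Table 6 could state the method), and on treating 267 restorations in 116 patients as independent. The last assumption affects every p-value above, adjusted or not.

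### The listed tests treat 267 restorations in 116 patients as independent; the survival p-value is the most exposed, and loss of significance is possible but not shown

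*Protocol*

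**What the plan says.** Under Participant selection, a patient qualified by "having at least one primary carious lesion (class I, II, or V) that requires restorative treatment", with no upper limit stated. At the last recall: "Finally, the last participation involved 116 patients, with 267 restorations being evaluated".

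The Statistical Analysis section lists the tests used:
- Between materials: "Chi-square and Fisher Exact tests were performed to assess differences between restorative materials".
- Over time: "Friedman and Wilcoxon Signed rank tests were performed to assess the effect of time on the restorations".
- Survival: "Kaplan-Meier and Long-rank tests were also performed to determine the overall survival rates of the restorations".

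Section 3.1 reports five EFHT failures (four lost, one fractured), one CR failure and no SF2 failure at 18 months. For the earlier visits it says: "No loss of retention or fracture was observed in any restoration at baseline and 6-month follow-up". It then concludes that "EFHT (94.2%) showed significantly lower retention than SF2 (100%) after 18 months", with p = 0.019, and that survival differs significantly among the materials; the text prints no p-value for survival. Percentages are per restoration, for example: "More restoration failures (de-bonding and fracture) were observed in class II cavities (4.4%) regardless of restorative material".

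The text mentions no patient-level unit, cluster adjustment, frailty term or mixed model. It does not say whether a patient received one material or several.

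**The concern.** Restorations in one mouth share hygiene, bite and saliva, so their outcomes may be correlated. Chi-square, Fisher and log-rank tests in standard form count each restoration as an independent observation. Friedman and Wilcoxon tests do pair the visits of one restoration, but still treat two restorations of one patient as unrelated.

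Two conclusions are at stake: the lower retention of EFHT than SF2, and the significant survival difference. Both rest on the same six failures. Having few events is not itself the error, but it makes both p-values sensitive to the unit of analysis.

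**Working it through.** **1. Cluster size.** 267/116 = 2.302 restorations per patient.

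**2. Group sizes, back-solved from section 3.1.** Five failures at 94.2% retained allow only EFHT n = 86 (81/86 = 94.2%). One failure at 98.8% allows CR n = 80 to 86. SF2 is then 267 − 86 − CR = 95 to 101.

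**3. Reproducing p = 0.019.** A two-sided Fisher test at restoration level, 5/86 against 0/101, gives p = 0.0193. Over all compatible splits the range is 0.0193 to 0.0227. Other percentages use the same unit: class II failures number 2 + 1 + 1 = 4, and 4.4% is 4/90 or 4/91; 3.2% is 1/31 (section 3.5); 7.5% is 3/40 (section 3.8). The match agrees with a restoration-level analysis but does not alone prove one.

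**4. Reconstructing the log-rank test.** All failures were found at 18 months, so if each is timed at that recall the test reduces to one table: 5/86, 1/80, 0/101. Expected failures are 1.93, 1.80 and 2.27. Pearson chi-square is 7.665; multiplied by 266/267 it is 7.636 on 2 df, p = 0.0220 (0.0220 to 0.0224 over the seven splits).

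**5. Design effect, assuming one material per patient.** DEFF = 1 + (2.302 − 1) × ICC, and the chi-square is divided by DEFF.

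| Assumed ICC | DEFF | Chi-square | p |
|---|---|---|---|
| 0.1 | 1.130 | 6.756 | 0.034 |
| 0.2 | 1.260 | 6.059 | 0.048 |
| 0.3 | 1.391 | 5.491 | 0.064 |

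The 5% critical value is 5.991, so the crossing is at ICC = (7.636/5.991 − 1)/1.302 = 0.21. With six events this is a rough guide.

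**6. Type I error of nominal 5% tests.** Simulation with 20,000 runs at the pooled failure rate 6/267 = 2.2%; ranges run over near-equal to very uneven cluster sizes.

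| Allocation (assumed) | Test | ICC 0.1 | ICC 0.2 | ICC 0.3 |
|---|---|---|---|---|
| One material per patient | Log-rank | 5.2–7.3% | 7.4–10.9% | 8.9–15.0% |
| One material per patient | Fisher | 2.7–4.0% | 3.8–5.3% | 4.6–8.0% |
| Mixed within patients | Log-rank | 3.0–3.2% | 2.4–2.6% | 1.6–2.1% |
| Mixed within patients | Fisher | 1.7% | 1.2–1.4% | 1.0% |

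**7. How many patients carry the EFHT failures.** Patient-level Fisher p-values, one material per patient, by the number of patients holding the five failures:

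| Assumed patients, EFHT vs SF2 | 5 | 4 | 3 | 2 |
|---|---|---|---|---|
| 37 vs 44 (116 × 86/267 and 116 × 101/267) | 0.017 | 0.040 | 0.091 | 0.21 |
| 40 vs 41 | 0.026 | 0.055 | 0.12 | 0.24 |
| 40 vs 40 | 0.055 | 0.12 | 0.24 | 0.49 |

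The first column involves no shared failures at all, yet runs from 0.017 to 0.055. The table therefore shows how much the answer depends on unreported counts. It does not measure the effect of clustering.

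**The case against.** A reader might infer that the retention and survival p-values are simply invalid, or that significance disappears once patients are respected. The documents support neither. Step 6 shows Fisher at or below about 5% up to ICC 0.2, exceeding it clearly only with high correlation and uneven clusters. With mixed allocation both tests are conservative, so reported significance would not be exaggerated. Clear inflation is confined mainly to the log-rank test with one material per patient.

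The assumed correlations are also large for a rare event. At a 2.2% failure rate, ICC 0.21 means that a second restoration fails with probability 0.21 + 0.79 × 0.022 = 0.23 once the first has failed, about ten times the baseline. Nothing in the protocol supports or excludes that. The group sizes are derived, and the flow diagram and tables, which are not shown here, might state the allocation. No time-effect result is shown to be affected.

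A blanket switch to a within-patient permutation would be unsound too. It is coarse: a 5–0 split in five patients with one EFHT and one SF2 restoration each gives 2 × 0.5⁵ = 0.0625, and a 5/1/0 split over six patients with all three materials gives 39/729 = 0.053. It also requires exchangeable assignment, which the text does not establish.

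These points limit the size of the concern and shape the remedy. They do not remove it: the patients are clusters by the protocol's own count, the listed tests ignore this, and these are tests reported as performed, with conclusions drawn from them, not details left for a later plan.

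**Conclusion.** The concern holds in limited form and should be fixed. The listed tests use the restoration as the independent unit although patients averaged 2.30 each. With within-patient correlation the p-values are miscalibrated, and the direction cannot be fixed without the allocation. Assuming one material per patient, the reconstructed survival p of 0.022 rises to about 0.034, 0.048 and 0.064 at ICC 0.1, 0.2 and 0.3. Under the same assumption the retention p = 0.019 roughly holds its error rate up to ICC about 0.2. With mixed allocation both are conservative. The ICC, the allocation, the patients per material and the patients carrying failures are all assumptions. The percentages by material stand, and the p < 0.001 colour results are unlikely to change.

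**What to change.** 1. Report how materials were allocated between and within patients, and how many distinct patients carry the six failures, by material.
2. Re-analyse retention and survival with a method that respects the patient. If each patient had one material, permute whole patients and base the significance statements on that result. Permutation also copes with the absence of SF2 failures.
3. If materials were mixed, give a patient-clustered or within-patient analysis beside the restoration-level result. Say that the restoration-level result is likely conservative and that a within-patient permutation is coarse with six events. Do not replace the p-value by that permutation alone.
4. Use patient-clustered GEE for outcomes with enough events, such as colour match and anatomic form. Report outcomes with no event or a single event descriptively.

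The cost is a re-analysis of existing data. It needs the link from each restoration to its patient, which is assumed recoverable because patients were counted at each recall. Some p-values may become less favourable, and a within-patient analysis uses only patients with more than one material, so it may lose significance through low power alone.
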